- 6 Only in females of childbearing potential.
- 7 Urinary dipstick including pH, protein, glucose, ketone, RBCs, and WBCs. Quantitative measurement only if positive dipstick. Urinalysis includes also (at Visits V1, V2, V4, and V6) urinary microalbumin, creatinine, and microalbumin/creatinine ratio (spot sample, morning void).
- 8 Haematology panel/RBC indices sampled at pre-dose (trough) include: Hb, reticulocytes (abs, %), RBC count, HCT, MCH, MCV, MCHC, RDW, % hypochromic RBC, CHCM, WBC, neutrophils (abs, %), lymphocytes (abs, %), monocytes (abs, %), eosinophils (abs, %), basophils (abs, %), and platelets. At screening/Visit V1, only Hb and reticulocytes will be assessed.
- 9 Serum chemistry sampled at pre-dose (trough) includes calcium, sodium, magnesium, potassium, phosphorus, chloride, bicarbonate, blood urea nitrogen, uric acid, creatinine kinase, creatinine, folic acid, albumin, total protein, globulin (calculated), alanine transaminase, aspartate transaminase, alkaline phosphatase, glucose, triglycerides, and cholesterol.
- 10 Haemolysis markers sampled at pre-dose (trough) include LDH, free haptoglobin, and direct/total bilirubin (indirectly calculated).
- 11 Endothelial inflammation/dysfunction markers sampled at pre-dose (trough) include hsCRP, IL-1, IL-6, TNF-alpha, sP-selectin, sVCAM-1, xanthine oxidase, and endothelin-1.
- 12 Iron-related parameters/markers of erythropoiesis sampled at pre-dose and 2 hours post- morning dose include total serum iron, serum ferritin, transferrin, TSAT, hepcidin, and erythropoietin. At Visit V1, serum ferritin, TSAT, and TIBC will be sampled for exclusion criteria only.
- 13 PK samples are collected on Visit V4 at pre-dose, and 2 hours (± 15 minutes), 4 hours (± 30 minutes), and 6 hours (± 30 minutes) post-dose.
- 14 At Visit V2, the subject will be asked for VOC episodes within the last 8 weeks. At Visits V3, V4, V5, and V6, the subject will be asked for VOC episodes (number of events and pain intensity (NRS: 0-10) compared to historical VOC episodes) since previous visits. Visceral infarctions will be assessed as per standard of care.
- 15 For more details see the respective visit in Section 8 of CSP.

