Percentages will be calculated using the total subjects per randomised treatment group, except for outputs in the PPS and the safety set, where percentages are based on the total subjects per actual treatment group.

5.1.2 *Definition of Baseline*

The baseline value for a variable will be defined as the last available (non-missing) value before the first administration of study drug. Study day 1 is defined as the day of the first study drug administration. For analysis relative day, if considered date is before the first study drug administration date, then analysis relative day will be computed as date minus first study drug administration date, otherwise, it will be computed as date minus first study drug administration date + 1.

5.1.3 *Planned Assessment Windows*

Table 4 describes the analysis visit windows (i.e. the relative study day ranges) to be applied to the assessments or sample collections dates to determine the analysis visit.

Table 4 Planned and Analysis visits Windows

Analysis Visit Label	Target Day	Planned Visit Window (Protocol Specified)	Analysis Visit Window
Baseline	1	--	Before first IMP intake
Visit 3 (Day 14)	14	± 2 days	From Day 2 to Day 21
Visit 4 (Day 28)	28	± 4 days	From Day 22 to Day 35
Visit 5 (Day 42)	42	± 4 days	From Day 36 to Day 49
Visit 6 (Day 56)	56	± 4 days	From Day 50 to Day 70
Visit 7 (Day 84)	84	± 4 days	From Day 71 and higher

Assessments (planned and unscheduled) will be re-mapped into the analysis windows. For a parameter, the following rules will be applied:

- if several assessments fall into the same analysis window, the closest to the target day will be considered for the analysis.
- When there are 2 assessments closest to the target day, the latest one will be considered for the analysis.
- if several assessments are available at the selected day, the average of the values will be taken.

In all statistical tables by visit, the analysis visits will be considered. In listings presenting data by visit, both nominal and analysis visits will be provided.

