All laboratory results (serum biochemistry, safety haematology and urinalysis) will be listed, including all unscheduled visits for the aITT.

In addition, listings will be provided for urine Pregnancy Test and for hemoglobin local laboratories measurements.

5.8.3 *Electrocardiogram (ECG) Evaluations*

PR interval (ms), QRS duration (ms), QT interval (ms), RR interval (ms), QTcF (ms) interval and ventricular rate (bpm) will be evaluated at each visit at pre-dose and 2 hours (± 30 minutes) post-morning dose.

QT corrected using Fridericia formula is defined as:

$$QTcF(ms) = QT(ms) / \sqrt[3]{RR\ (ms)}$$

Pre-dose and 2 hours post morning dose values will be described by visit from baseline as well as changes from baseline (pre first dose measures) to each post baseline measures at pre-dose and at 2 hours post morning dose for all parameters by actual treatment groups on the safety set. For tabulations, analysis windows (see Section 5.1.3) will be considered for each visit but no window will be considered for the time-points (pre or 2 hours post-dose).

For each ECG parameter, the following figure will be provided: individual values (y-axis) in function of target visit day and time-point (nominal x-axis scale: "D1", "D1+2h etc...") joined by subject and plotted in separate windows for the randomised cohorts (1, 2, 3, 4) and for overall subjects randomised in VIT-2763 (5-window panel plot). All graphics will be done on the Safety set.

All ECG parameters results will be listed with changes from baseline as well as overall ECG interpretation on the aITT.

5.8.4 *Vital Signs and Body Weight Evaluations*

The values and changes from baseline results of Systolic Blood Pressure (SBP) (mmHg), Diastolic Blood Pressure (DBP) (mmHg), pulse rate (bpm) and body weight (kg) will be summarised by visit by actual treatment groups on the safety set. For tabulations, analysis windows (see Section 5.1.3) will be considered for each visit.

Vital sign results with changes from baseline will be presented for individual subjects in data listings on the aITT.

5.8.5 *Physical Examinations*

All clinically significant abnormalities in physical examination will be collected in the general medical history or the adverse event eCRF pages as appropriate. Therefore, no specific analysis of physical examination will be performed.

5.9 *Other Analyses*

5.9.1 *Iron-related parameters and blood inflammatory markers*

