Iron-related parameters include total serum iron, serum ferritin, transferrin, TSAT, hepcidin and erythropoietin.

Blood inflammatory markers include high sensitivity C-reactive protein, interleukin 1 and interleukin 6, tumour necrosis factor alpha, soluble vascular cell adhesion molecule 1, endothelin-1, soluble platelet-selectin, and xanthine oxidase.

All data will be reported in SI. For analysis purposes, values preceded by a “<” or a “>” sign (i.e. those below or above the limits of quantification) will be considered equal to the lower or upper limit of quantification, respectively.

For all iron-related parameters and blood inflammatory markers, standard descriptive statistics for continuous variables will be tabulated for the values by visit (including baseline) and for changes from baseline by post-baseline visit for randomised treatment groups as described in Table 5 on the ITT. Analysis windows (see Section 5.1.3) will be considered for each visit.

Analyses will be repeated on the PPS by actual treatment group if it differs and on mITT if applicable.

For each iron-related parameter and blood inflammatory marker, the following figure will be provided: individual values (y-axis) in function of target visit day (x-axis) joined by subject and plotted in separate windows for the randomised cohorts (1, 2, 3, 4) and for overall subjects randomised in VIT-2763 (5-window panel plot). All graphics will be done on the ITT.

Finally, all parameter results with changes from baseline will be listed, including all unscheduled visits, for the aITT.

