5.9.4 VOC Episode and Visceral Infarctions

The number of VOC episodes occurring over 8 weeks of treatment will be computed as the number of VOC episodes collected with a start date in the 60 days after baseline (corresponding to the target day 56 of the end of treatment visit plus the 4 days of visit window allowed in protocol).

The number of visceral infarctions occurring over 8 weeks of treatment will be computed as the sum of the number of visceral infarction collected at Visit 3, Visit 4, Visit 5 and Visit 6 (number of infarction since last visit collected at each visit in CRF).

Episodes counts will be categorized as:

- 0
- 1
- 2
- >2

Shift tables summarising the number of VOC episodes and the number of visceral infarctions in categories in the 8 weeks after baseline versus 8 weeks prior baseline will be provided.

The number of VOC episodes occurring over 4 weeks after end of treatment will be computed as the number of VOC episodes collected with a start date in the 28 days after treatment stop date.

The number of visceral infarctions occurring over 4 weeks after end of treatment will be the number of visceral infarction collected at Visit 7.

The number of VOC episodes occurring over 4 weeks after end of treatment, the number of visceral infarctions recorded at each visit and occurring over 4 weeks after end of treatment will be listed on the aITT. Each VOC episode with its pain intensity (NRS: 0-10) will be described by visit in a listing.

The ITT population will be used, and summaries will be repeated on the PPS as well.

5.9.5 *Pharmacokinetics Analyses*

Sparse sampling for determination of VIT 2763 plasma concentration following multiple dosing will be obtained from pre-dose trough to 2, 4 and 6 hours post-morning dose at study Visit 4 (V4).

The population pharmacokinetic analysis will be described in a separate analysis plan.

Pharmacokinetic plasma concentration of VIT-2763 will be summarised for the ITT and listed by subject for the aITT for each sampling time point by visit for cohorts 1, 2 and 3 (Placebo group not displayed), using descriptive statistics (including geometric mean and CV%, arithmetic mean, standard deviation, arithmetic CV%, median, maximum, minimum, and N). No formal statistical tests are planned.

The observed plasma concentration-time profiles will be plotted by subject using spaghetti plots for cohorts 1, 2 and 3.

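### As written, the SAP averages the pre-dose and 2-hour iron samples into one value per visit and leaves the Day 1 2-hour sample out of every by-visit iron table

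*SAP*

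**What the plan says.** The SAP schedule of events (Table 3, footnote 12) has "Iron-related parameters/markers of erythropoiesis sampled at pre-dose and 2 hours post- morning dose include total serum iron" and five further parameters. Protocol Sections 8.2 to 8.6 place both draws on the same day at Visits 2 to 6. Section 8.7 has a single draw at Visit 7.

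For these parameters SAP 5.9.1 states that "standard descriptive statistics for continuous variables will be tabulated for the values by visit (including baseline) and for changes from baseline by post-baseline visit", and adds that "Analysis windows (see Section 5.1.3) will be considered for each visit". The accompanying figure shows "individual values (y-axis) in function of target visit day (x-axis) joined by subject and plotted in separate windows for the randomised cohorts". Neither the tables nor the figure names a time point.

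SAP 5.1.3 works parameter by parameter. Its last rule is that "if several assessments are available at the selected day, the average of the values will be taken". In Table 4 of that section the Baseline window closes at the first intake and the Visit 3 window opens on Day 2.

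ECG has the same two-time-point design but is handled differently. SAP 5.8.3 describes pre-dose and 2-hour values separately and says the windows "will be considered for each visit but no window will be considered for the time-points (pre or 2 hours post-dose"). Its figure plots "individual values (y-axis) in function of target visit day and time-point". In SAP 5.9.5, plasma concentrations are summarised "for each sampling time point by visit for cohorts 1, 2 and 3".

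**The concern.** The two iron samples measure different things. One shows how much restriction is left at the end of a dosing interval, the other the early response to a dose. Protocol 2.3.3 attributes the absence of a haematological effect in the earlier thalassaemia study to iron restriction lapsing between doses. It says the BID and TID regimens are there to explore different peak-to-trough patterns. Protocol 1.4.2 adds that the same study showed PK and PD samples were needed at more time points. Protocol 8.8 requires the pre-dose iron sample to be taken before dosing, although several other blood samples may move to after the dose from Visit 3 on.

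A single averaged value removes the distinction that this sampling was set up to capture. Three comparisons suffer:

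- The pre-dose contrast between BID and TID is diluted by the 2-hour values.
- The averages cannot be set beside the earlier study's TSAT changes, which are stated at about 2 hours after dosing.
- On-treatment averages are not like for like with the baseline, which is pre-dose only, or with the single Visit 7 sample.

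**Working it through.** The plan gives no figure to reproduce. The check applies the SAP rules to the sampling schedule.

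**Inputs**

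- Draws: pre-dose and 2 hours at Visits 2 to 6, one at Visit 7 (protocol Table 1 footnote 13; Sections 8.2 to 8.7).
- Parameters: six (SAP 5.9.1). Planned subjects: 24 (SAP 2.2).
- Day 1 is the day of first dose, and baseline is the last value before it (SAP 5.1.2).
- Windows from SAP Table 4, as shown below.
- Earlier study's TSAT change at about 2 hours: −46.8% for BID (protocol 2.3.3).

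**Step 1: map each draw at its target day**

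| Draw | Window | Tabulated as |
|---|---|---|
| Day 1 pre-dose | Baseline (before first intake) | single value |
| Day 1, 2 h | none: after first intake, before Day 2 | not tabulated |
| Day 14 pre-dose and 2 h | Visit 3 (Days 2–21) | one average |
| Day 28 pre-dose and 2 h | Visit 4 (Days 22–35) | one average |
| Day 42 pre-dose and 2 h | Visit 5 (Days 36–49) | one average |
| Day 56 pre-dose and 2 h | Visit 6 (Days 50–70) | one average |
| Day 84 | Visit 7 (Day 71 on) | single value |

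**Step 2: count, assuming complete data**

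- Visits 3 to 6, per subject and parameter: 4 × 2 = 8 draws give 4 values.
- All draws after first dose: 1 + 8 + 1 = 10 give 4 + 1 = 5 values.
- Whole trial, Visits 3 to 6: 24 × 6 × 8 = 1,152 results give 24 × 6 × 4 = 576 values.
- Day 1, 2 hours: 24 × 6 × 1 = 144 results in no by-visit table.

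**Step 3: effect on a comparison of regimens**

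Let p1 and p2 be the pre-dose values and q1 and q2 the 2-hour values in two regimens. The displayed difference is

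(p1 + q1)/2 − (p2 + q2)/2 = [(p1 − p2) + (q1 − q2)]/2.

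If q1 = q2 and p1 − p2 = d, this equals d/2. An assumed d of 10 points is shown as 5, and 20 as 10.

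By the nominal clock in protocol 6.3.2, the pre-dose sample falls 24 − 12 = 12 h after the last BID dose and 24 − 16 = 8 h after the last TID dose. In Cohorts 2 and 3 the 2-hour sample follows the same 120 mg dose.

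**Step 4: illustration on the TSAT scale**

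The documents give no trough value, so the pre-dose change is assumed to lie between 0 and the 2-hour change of −46.8%.

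- No pre-dose change: (0 − 46.8)/2 = −23.4%.
- Pre-dose change equal to the 2-hour change: (−46.8 − 46.8)/2 = −46.8%.
- Flat profile at −23.4%: (−23.4 − 23.4)/2 = −23.4%.

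The first and third profiles are a full swing and no swing. The table would show the same number for both.

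**The case against.** **Tie rule.** The rule just before the averaging rule in SAP 5.1.3 takes the later of two assessments equally near the target day. Two same-day samples could be read as such a tie, in which case the 2-hour value is kept and nothing is averaged. The averaging rule, however, addresses several values on the selected day, so the tie rule is best read as covering two different days. On the other reading the averaging arithmetic falls away, but pre-dose values vanish from the tables and Day 1 at 2 hours still has no window.

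**Day 1 sample.** The iron endpoint is defined after 2, 4, 6 and 8 weeks and 4 weeks after end of treatment, so the Day 1 2-hour sample is not part of it. That is correct. The point is only that a scheduled sample reaches no by-visit summary.

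**Counts.** In healthy volunteers (protocol 1.4.1) ferritin, transferrin and erythropoietin showed no dose-related effect. Restricted to serum iron, TSAT and hepcidin, the counts halve: 24 × 3 × 8 = 576 results become 288, and 24 × 3 = 72 Day 1 results are untabulated. The rule still applies to all six.

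**Size of dilution.** The d/2 result needs equal 2-hour values. If the pre-dose difference persists at 2 hours, the displayed difference approaches d. The zero trough in the illustration is likewise an assumption. Both stand as limits on size, not on the mechanism.

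**Partial coverage.** The volunteer study saw the fall in iron and TSAT at 4 to 12 hours, so two samples describe the 24-hour pattern only in part. That is true, but it is no reason to merge them.

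**Status of the outputs.** Protocol 12.10 asks only for summaries by visit, all analyses are descriptive (SAP 3.2), and the listings keep every result. SAP 5.1.3 ties analysis visits to tables, so averaging in the figure is not established; the figure lacks a time-point axis all the same. The table shells are not among the documents and may already split the samples. If they do, the SAP text should say so.

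**Conclusion.** The concern holds. Under the SAP as written, the pre-dose and 2-hour iron samples at Visits 3 to 6 become one average per visit, and the Day 1 2-hour sample enters no by-visit table. This follows from a stated rule, and the separate treatment of ECG and PK shows that the SAP names time points when it wants them kept apart.

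The counts assume complete data on the planned 24 subjects. Halving of a pre-dose difference assumes equal 2-hour values, and the TSAT range assumes a trough that the documents do not give.

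The consequence is confined to exploratory, descriptive tables. It merits correction because those tables bear directly on the dose rationale, but it does not touch the primary or secondary endpoints.

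**What to change.** - In SAP 5.9.1, summarise and plot the iron-related parameters by visit and nominal time point (pre-dose and 2 hours), each as change from the pre-first-dose baseline, with a Day 1 2-hour row. SAP 5.8.3 offers the model.
- In SAP 5.1.3, limit same-day averaging to repeat samples at the same nominal time point, and state that the tie rule concerns different days.
- Optionally, add the within-visit change (2 hours minus pre-dose).

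The cost is a few SAP sentences and some extra table rows. No new samples or data are needed.

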5.1.4 Treatment Start/Stop Dates

Treatment start date is collected at baseline visit in the study treatment administration form of the CRF. If there is no treatment date available in this CRF page, date of randomisation will be imputed as the start of treatment date, if it is known that the subject received study drug (information recorded in the study treatment administration page or in patient supply accountability log page of the CRF or any information from monitoring).

Treatment stop date is collected in the treatment termination form of the CRF. If the date of last intake of study medication is missing in this form, the latest start date from study treatment administration page (CRF does not record the end date) would be used to impute end of treatment date.

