4.3 Per-Protocol Set

The per-protocol set (PPS) consists of all subjects who, in addition to the ITT criteria, completed the study and had no major protocol deviations impacting the primary objective of the trial (as defined in the protocol deviation plan and finalised during the blind data review meeting). Subjects with a study drug compliance (see Section 5.6) lower than 80% of prescribed doses or upper than 110% of prescribed doses will be considered as major deviations.

Subjects who did not complete the study as per protocol as indicated in study termination CRF form or who discontinued the treatment prematurely as recorded in treatment termination form will be considered as not having completed the study and will then be excluded from PPS in addition to subjects with major protocol deviations. The subjects will be analysed based on the treatment they were randomised to.

4.3.1 *Protocol deviations*

All subjects with major protocol deviations impacting the primary objective as defined in the latest protocol deviations plan will be excluded from PPS. They will be reviewed during the blind data review meeting.

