For treatment group dose intake day missing (or Unknown), the day will be imputed to the end day of the previous visit.

The original incomplete, missing or partial dates and corresponding imputed dates will be presented in the listings.

During the conduct of the study, a non-neglectable number of missing data for the primary endpoint (indirect bilirubin) have been observed at baseline and Visit 6. Sensitivity analyses will be performed for the primary endpoint with different imputations for the missing data. Only missing data due to haemolysed samples will be imputed as they can be considered as missing at random while missing data because of withdrawal of the study cannot. Imputations will be as following:

- Missing baseline data will be imputed with the median of the non-missing baseline indirect bilirubin of the pooled subjects of all cohorts.
- For missing data at visit 6, 3 types of imputation will be performed: the minimal value, the mean and the maximal value within the Cohort of the subject.

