5.6 Study Drug Exposure and Compliance

The following durations of study drugs (including VIT-2763 and Placebo) will be computed in days:

Duration of study drug (in days) = Treatment stop date – Treatment start date + 1

Treatment start and stop dates will be derived as defined in Section 5.1.4.

The total amount of VIT-2763 taken in mg will be calculated for each subject from the difference between the amount of VIT-2763 dispensed in mg and the amount of VIT-2763 returned in mg. It will be compared to the amount expected to be taken for subjects randomised in a VIT-2763 cohort to calculate the percentage compliance to VIT-2763. Derivation details are provided below.

Total amount of VIT-2763 (mg) = $30 * (\text{Number of VIT-2763 30 mg capsules dispensed} - \text{Number of VIT-2763 30 mg capsules returned}) + 60 * (\text{Number of VIT-2763 60 mg capsules dispensed} - \text{Number of VIT-2763 60 mg capsules returned})$.

The total amount of VIT-2763 taken will be computed for all randomised subjects and will be equal to 0 if no dispensation error occurred in Placebo cohort. In case of miss allocation for a patient receiving VIT-2763 instead of Placebo, the amount will be counted for VIT-2763.

Expected amount of VIT-2763 (mg) for cohort 1 = $120 * (\text{Duration of study drug in days} - 1) + 60$.

Expected amount of VIT-2763 (mg) for cohort 2 = $240 * (\text{Duration of study drug in days} - 1) + 120$.

Expected amount of VIT-2763 (mg) for cohort 3 = $360 * (\text{Duration of study drug in days} - 1) + 120$.

VIT-2763 compliance (%) = $(\text{Total amount of VIT-2763 (mg)} / \text{Expected amount of VIT-2763 (mg)}) \text{ for cohort 1-2-3} * 100$.

The total number of capsules of study drug (VIT-2763 or Placebo) taken will be calculated for each subject from the difference between the total number of capsules dispensed and the total number of capsules returned. It will be compared to the expected number of capsules to be taken by subject to calculate the percentage compliance to study drug.

Total amount of study drug (number of capsules) = Number of capsules dispensed - Number of capsules returned

Expected amount of study drug (number of capsules) for cohorts 1, 2, 4a = $4 * (\text{Duration of study drug in days} - 1) + 2$

Expected amount of study drug (number of capsules) for cohort 3, 4b = $6 * (\text{Duration of study drug in days} - 1) + 2$

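### If the last-dose date is missing, the SAP ends treatment at the latest dosing start date but still counts every unreturned capsule as taken, so compliance can be inflated and exposure shortened

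*SAP*

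**What the plan says.** SAP 5.1.4 names a source for each end of treatment. For the start, "Treatment start date is collected at baseline visit in the study treatment administration form of the CRF". For the stop, "Treatment stop date is collected in the treatment termination form of the CRF". Only if that last-intake date is blank does the fallback apply: "the latest start date from study treatment administration page (CRF does not record the end date) would be used" as the end of treatment.

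SAP 5.6 takes these dates over: "Treatment start and stop dates will be derived as defined in Section 5.1.4". Duration is stop minus start plus 1, and expected capsules are a function of duration. Capsules taken are those dispensed minus those returned, with no reference to the stop date.

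Two later rules depend on the result. In SAP 4.3, compliance "lower than 80% of prescribed doses or upper than 110% of prescribed doses will be considered as major deviations", which removes the subject from the per-protocol set (PPS). In SAP 5.9.4, the post-treatment VOC count is the number of "VOC episodes collected with a start date in the 28 days after treatment stop date".

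SAP 5.1.9 has a further sentence: "For treatment group dose intake day missing (or Unknown), the day will be imputed to the end day of the previous visit". It does not say how this relates to 5.1.4.

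**The concern.** A start date on a page that holds no end dates marks the beginning of a dosing record. Used as the stop date, it assumes that nothing was taken afterwards. The capsule count makes no such assumption: whatever was dispensed for the last interval and not returned counts as taken. The ratio then sets capsules from a longer period against an expectation for a shorter one.

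Three outputs are at stake: the exposure and compliance tables on the ITT population, PPS membership through the 80% and 110% limits, and the start of the 28-day post-treatment VOC window. The primary analysis is repeated on the PPS, and each active cohort has 6 planned subjects, so one misclassified subject is a sixth of an arm.

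**Working it through.** The plan states no compliance figure to reproduce, so the check applies its own formulas.

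**Inputs**
- Expected capsules for duration D (SAP 5.6): 4 × (D − 1) + 2 for BID; 6 × (D − 1) + 2 for TID.
- Visit 5 at Day 42 ± 4 and Visit 6 at Day 56 ± 4 (SAP Table 4).
- Last dispensing at Visit 5; the Visit 6 morning dose is taken at site (Protocol 8.5 and 8.6).
- Assumption: the termination-form date is blank. The documents do not say how often this happens.

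**Formula check.** Full adherence with stop date Day 56:
- BID: 4 × 55 + 2 = 222 taken, 222 expected, 100%.
- TID: 6 × 55 + 2 = 332 taken, 332 expected, 100%.

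The formulas are sound when the stop date is right.

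**Latest row at Visit 5, Day 42; every capsule taken to the morning of Day 56**
- BID expected: 4 × 41 + 2 = 166. Compliance 222/166 = 133.7%.
- TID expected: 6 × 41 + 2 = 248. Compliance 332/248 = 133.9%.
- The mg formulas agree. Cohort 1: (120 × 55 + 60)/(120 × 41 + 60) = 6660/4980 = 133.7%. Cohort 3: (360 × 55 + 120)/(360 × 41 + 120) = 19920/14880 = 133.9%.
- Duration reads 42 days instead of 56.

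**Range when both visits move within their windows**

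| Latest row | True last dose | Days lost | BID | TID |
|---|---|---|---|---|
| Day 46 | Day 52 | 6 | 206/182 = 113.2% | 308/272 = 113.2% |
| Day 42 | Day 56 | 14 | 222/166 = 133.7% | 332/248 = 133.9% |
| Day 38 | Day 60 | 22 | 238/150 = 158.7% | 356/224 = 158.9% |
| Day 56 (Visit 6 row) | Day 56 | 0 | 222/222 = 100% | 332/332 = 100% |

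Every Visit 5 case for a fully adherent subject exceeds 110%. At the other extreme, a page holding only the baseline row gives D = 1 and 2 expected capsules: 222/2 = 11,100% for BID.

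**What the PPS limits then select (Day 42 row, Day 56 last dose, BID).** The inflation factor is 222/166 = 1.337. A displayed 80% is a true 80/1.337 = 59.8%; a displayed 110% is a true 110/1.337 = 82.3%. A completer truly between about 60% and 80% would be kept, and one above about 82% would be flagged. TID gives the same to within 0.2 points.

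**Subject lost after Visit 5.** No Visit 6 row can exist, whatever the form layout. Suppose, as an assumption, that exactly 14 days of capsules were dispensed at Visit 5 and none came back. For BID this adds 4 × 14 = 56 to 166, giving 222 counted as taken against 166 expected: again 133.7%.

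**VOC window.** With a true stop at Day 56 the window is Days 57 to 84. With an imputed stop at Day 42 it is Days 43 to 70. Of those 28 days, 14 (Days 43 to 56) are on drug if dosing continued to Day 56, and Days 71 to 84 drop out. Days 43 to 60 also fall in the 60-day on-treatment count. Days 57 to 60 overlap with that count even when the stop date is right, so the rule adds the other 14 days.

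**The case against.** This is a fallback, and a Visit 6 row may well exist. The termination form is the primary source, blank fields raise queries (Protocol 15), and the protocol requires the Visit 6 morning dose to be taken at site. The SAP 5.6 formulas end on one morning dose, which fits. If site doses create rows, the rule returns the true date for a completer and the error vanishes. This stands: a reader might infer that compliance is wrong for every subject whose stop date is imputed, and the documents do not support that. They do not settle the layout the other way either. The protocol expressly requires an eCRF administration time only for the first dose, and SAP 5.1.4 mentions the administration form only in connection with baseline.

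The PPS effect is also narrow. SAP 4.3 already excludes subjects who stopped treatment early or did not complete, so only a completer with a blank date and no Visit 6 row is exposed, and deviations are reviewed blind before unblinding.

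The VOC effect is limited: post-treatment VOC counts are listed, not tabulated. A reader might infer that the post-treatment safety summaries shift as well. They do not: the adverse-event selections use fixed day counts, and post-treatment infarctions come from Visit 7.

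Finally, 5.1.9 might be read as contradicting 5.1.4. That is not established. One concerns a missing day of intake and the other a missing last-intake date, so they may be complementary. What is missing is a statement of scope.

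**Conclusion.** The point holds as a conditional defect in a stated rule. Whenever the latest administration row precedes the true last dose, duration and expected capsules are too small while capsules taken are unchanged. For a fully adherent subject dosed to Visit 6 with a latest row at Visit 5, compliance reads about 134% on target days and 113% to 159% across the windows, with 6 to 22 days of exposure lost. With a Visit 6 row there is no error.

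For completers, the consequence is possible misclassification at the PPS limits in either direction. For subjects lost to follow-up, who are outside the PPS anyway, the ITT exposure and compliance tables are distorted, and the listed VOC window can open while the subject is still on drug. The primary ITT analysis is not affected, because it uses visit windows rather than the stop date. The study is descriptive, so no test or decision rule is at risk.

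The size rests on assumptions that the documents leave open: that termination-form dates are missing for some subjects, and which visits create rows on the administration page.

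**What to change.** In SAP 5.1.4:
- State which visits populate the administration page.
- Impute a missing last-intake date from the latest evidence of dosing: the Visit 6 or early-termination on-site dose if given, otherwise the latest accountability or contact evidence. Keep any recorded month and year.

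In SAP 5.6 and 4.3: where the stop date is imputed without a recorded last dose, report compliance as not evaluable and do not apply the 80% to 110% limits automatically. Decide PPS membership for these subjects at the blind data review. This matters because accountability or contact dates do not prove when the last capsule was taken, and unreturned capsules may not have been taken at all.

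In SAP 5.1.9: state the scope of the intake-day sentence relative to 5.1.4. Deleting it could leave partial intake dates without a rule.

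The cost is SAP wording and a small change to one derivation. Dispensing, return, visit and contact data are already collected.
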